7.6 Reporting Procedures

7.6.1 Unanticipated Problem Reporting

Incidents or events that meet the OHRP criteria for unanticipated problems require the creation and completion of an unanticipated problem report form. OHRP recommends that investigators include the following information when reporting an adverse event, or any other incident, experience, or outcome as an unanticipated problem to the IRB:

- Appropriate identifying information for the research protocol, such as the title, investigator's name, and the IRB project number;
- A detailed description of the adverse event, incident, experience, or outcome;

- An explanation of the basis for determining that the adverse event, incident, experience, or outcome represents an unanticipated problem;
- A description of any changes to the protocol or other corrective actions that have been taken or are proposed in response to the unanticipated problem.

To satisfy the requirement for prompt reporting, unanticipated problems will be reported using the following timeline:

- Unanticipated problems that are serious adverse events will be reported to the IRB, DSMB, and NCCIH within 7 days of the investigator becoming aware of the event.
- Any other unanticipated problem will be reported to the IRB, DSMB, and NCCIH within 14 days of the investigator becoming aware of the problem.
- All unanticipated problems should be reported to appropriate institutional officials (as required by an institution's written reporting procedures), the supporting agency head (or designee), and OHRP within one month of the IRB's receipt of the report of the problem from the investigator.

7.6.1 Adverse Event Reporting

SAEs that are unanticipated, serious, and possibly related to the study intervention will be reported to the DSMB, IRB, and NCCIH in accordance with requirements.

If any SAEs are reported, the PIs will be alerted immediately, as well as the IRB. If deemed necessary, members of DSMB will be alerted immediately. The PIs and/or IRB will decide if stopping criteria have been met. If they believe so, an ad hoc teleconference will be arranged by the DSMB Administrator. No other participants will be enrolled until after the teleconference, which will occur within 24 hours. Additionally, SAEs will be reported using the following timeline:

- Unexpected fatal or life-threatening AEs related to the intervention will be reported to the NCCIH Program Officer, and DSMB within 3 days of the investigator becoming aware of the event. Other serious and unexpected AEs related to the intervention will be reported within 7 days.
- Anticipated or unrelated SAEs will be handled in a less urgent manner but will be reported to the DSMB, IRB, and other oversight organizations in accordance with their requirements and will be reported to NCCIH on an annual basis.
- All other AEs documented during the course of the trial will be reported to NCCIH on an annual basis by way of inclusion in the annual report and in the annual AE summary which will be provided to NCCIH and to the DSMB. The DSMB Report will state that all AEs have been reviewed.

7.7 Follow-up for Adverse Events

The following applies only for non-serious adverse events; SAEs will follow the aforementioned policies for reporting and monitoring of serious adverse events.

For non-serious AE, if the AE has not resolved by the Day 14 follow-up, then depending on the type of AE (expected or unexpected) the research assistant will either continue to follow-up with the participant or consider Day 14 as the final Date of Resolution:

- If the AE reported is listed on the Adverse Event Report Form (Codes 1-12; as listed in **Table 10**) as a possible, expected AE, the research assistant will continue to follow-up the participant a minimum of every 4 days until the AE resolves to record the Date of Resolution.

- If the AE reported is listed as “Other” (Code 13), or unexpected, and the Principal Investigator AND participant considers the AE is not related/or is unlikely related to the intervention, the research assistant will not continue to follow-up past the Day 14 follow-up and will consider Day 14 as the final Date of Resolution.

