6.7.3 Completion/Final Evaluation

On the final follow-up at day 30, participants will provide the final sample and be queried for changes in baseline health and other adverse events.

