7.2 Methods and Timing for Assessing, Recording, and Analyzing Safety Parameters

Unanticipated problems will be recorded in the data collection system throughout the study.

Details of all expected and unexpected adverse events reported by participants during follow-up calls, spontaneously, or observed by research personnel must be recorded in the adverse event report forms. Participants will be provided with a daily diary with a list of the most likely possible adverse events (see **Table 10**), where they can document expected and other unexpected events not already listed. All non-serious adverse events will be reported to the IRB during continuing review. All AEs regardless of severity level will be evaluated by the DSMB during scheduled meetings.

If a participant reports an AE/SAE that does not yet have a Date of Resolution (ongoing) and is continuous (no more than two days without interruption) across two follow-up periods, this AE/SAE will be considered one event. The total duration of the AE/SAE will be collected but only one AE/SAE report form will be completed for this particular event. If the symptoms resolved for more than two days before recurrence, these will be reported as separate events.

The study staff will record all reportable events with start dates occurring any time after informed consent is obtained until 7 (for non-serious AEs) or 30 days (for SAEs) after the last day of study participation. At each study visit, the study staff will inquire about the occurrence of AE/SAEs since the last visit. Events will be followed for outcome information until satisfactory resolution or stabilization. In the event of SAEs, all clinical and laboratory investigations considered necessary by the investigator will continue until values have returned to normal. The investigator will provide the IRB with copies of results of examinations and treatment carried out during the follow-up of SAEs. These reports will be provided to the FDA and the NCCIH Program Official.

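### Section 7.7 gives certain adverse events known to be ongoing a Day 14 resolution date, which falsifies their recorded end date and status and conflicts with Section 7.2

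*Combined protocol and SAP*

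**What the plan says.** Section 7.7 applies to a non-serious AE "if the AE has not resolved by the Day 14 follow-up" and then divides such events in two.

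- **Expected events (Codes 1-12, the Table 10 terms).** Here the instruction is that staff "will continue to follow-up the participant a minimum of every 4 days until the AE resolves to record the Date of Resolution".
- **Unexpected events (Code 13, 'Other').** A special rule applies on one condition: "the Principal Investigator AND participant considers the AE is not related/or is unlikely related to the intervention". In that case contact about the event stops and its record is closed; the stated instruction is that staff "will not continue to follow-up past the Day 14 follow-up and will consider Day 14 as the final Date of Resolution".

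Section 7.2 sets the general rules. On follow-up: "Events will be followed for outcome information until satisfactory resolution or stabilization". On counting, an AE that "does not yet have a Date of Resolution (ongoing) and is continuous (no more than two days without interruption) across two follow-up periods" is treated as a single event, with its total duration collected on one form. On recurrence: "If the symptoms resolved for more than two days before recurrence, these will be reported as separate events".

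Contact does not end at Day 14. Section 6.7.1 schedules follow-up calls at Days 7, 14 and 30, each within ±2 days. Under Section 6.7.3, participants at Day 30 will "be queried for changes in baseline health and other adverse events". Table 8 shows AE reporting running through Day 30.

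**The concern.** A resolution date should mean that the event ended. Here it is entered precisely when the event is known not to have ended. The record then carries a wrong date, a wrong outcome status and a shortened duration, and nothing marks the date as administrative. Anyone reading the listing later, including the data safety monitoring board (DSMB), cannot tell a true Day 14 resolution from an assigned one.

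Day 14 is also the last day of yogurt (Section 5.1), and Section 7.4.1 lists abatement on discontinuation among its guides to relatedness. A listing could therefore suggest that an event stopped with the yogurt when it did not, although the events concerned have already been judged not or unlikely related.

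The second issue is how the assigned date interacts with the counting rule in Section 7.2. Keeping a continuing AE as one event depends on there being no resolution date, and Section 7.7 supplies one. The plan does not say what to do when an event closed in this way is reported again at Day 30.

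**Working it through.** The plan gives no figure to reproduce. The check sets the rules side by side and adds simple date arithmetic.

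**1. Is the assigned date false?** The rule is triggered by non-resolution at the Day 14 follow-up (Section 7.7), and its output is a resolution date of Day 14. An event that meets the trigger cannot have resolved by that contact. The recorded end is wrong in every case unless the event happened to stop later that same day.

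**2. How much duration is lost?** For an event still present at the Day 30 contact, the loss is at least the time from the assigned date to that contact.

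| Case | Arithmetic | Minimum loss |
|---|---|---|
| Nominal days | 30 − 14 | 16 days |
| Late Day 14 contact, early Day 30 contact | 28 − 16 | 12 days |
| Early Day 14 contact, late Day 30 contact | 32 − 12 | 20 days |

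The last two rows take the assigned date to be the actual date of the Day 14 contact. If it is literally study Day 14, the range is 28 − 14 = 14 to 32 − 14 = 18 days, inside the same limits. An event that ends between the two contacts loses only the time from the assigned date to its true end.

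Illustration with an assumed onset on Day 10 and symptoms still present on Day 30: the recorded duration is 14 − 10 = 4 days; the true duration is at least 30 − 10 = 20 days.

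**3. Can one event become two?**

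- The one-event sentence in Section 7.2 requires that no resolution date exists and that the event is continuous, which I read as no symptom-free gap longer than two days. After Section 7.7 is applied, the first condition fails.
- The separate-event sentence requires symptoms that resolved for more than two days and then recurred. A continuous event does not meet this in fact. On recorded dates alone it appears to, because every gap in the table exceeds two days.
- A continuing event closed at Day 14 therefore fits neither sentence properly. Staff working from recorded dates could open a second event; staff who know that the symptoms never stopped could keep one.

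**4. Where do the records go?** Section 7.8.2 provides for AEs to be listed and summarised for the DSMB. Section 9 contains no analysis of AE duration. Substudy Addendum A (Appendix 3) concerns AEs related to the antibiotic course. Substudy Addendum B (Appendix 4) hypothesises about gastrointestinal AEs by sex and also refers to AEs generally.

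**The case against.** The strongest reply is that this is a narrow, prespecified exception with little consequence. It covers only non-serious, unexpected events that both the PI and the participant consider not or unlikely related. Blinded staff apply it, so nothing suggests that it favours an arm. No planned analysis uses duration. Section 7.2 itself accepts stabilization as an endpoint, so follow-up may properly end before an event resolves. All of that stands. It limits the importance of the point but does not make the recorded date true: ending follow-up and recording resolution are different things.

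Some stronger readings are tempting, and the documents do not support them:

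- **That AE counts are inflated.** A reader might infer this from the gap of more than two days. But the interval between contacts is not symptom-free time, and the separate-event sentence speaks of symptoms that actually resolved. Double logging is possible, not established.
- **That at least 16 days are always lost.** The visit windows bring the minimum down to 12 days, and only for events still present at the Day 30 contact.
- **That the substudy results are compromised.** Substudy A's outcome is antibiotic-related events, whereas the rule covers events judged not or unlikely related to the intervention. Substudy B's hypothesis concerns gastrointestinal events, most of which are Table 10 terms and so are followed to resolution. Some unlisted terms could be Code 13, so the overlap with B is small rather than nil.
- **That unexpected events judged related have no rule at all.** Neither branch of Section 7.7 covers them, or cases where PI and participant disagree, but Section 7.2's general rule can be read as applying. The text should say so.

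**Conclusion.** The point holds in a limited form. For the events in its scope, Section 7.7 records a resolution date and status that the study team knows to be wrong and shortens a duration that Section 7.2 says will be collected. For an event still present at the Day 30 contact, the shortfall is at least 12 to 20 days depending on visit timing, nominally 16. The two sections conflict on when follow-up ends, and together they leave it unclear whether a Day 30 report is the same event or a new one.

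The effect is confined to AE listings and summaries: the DSMB reports and, to a small extent, Substudy B. The primary acetate analysis, power and alpha are unaffected. The number of events affected cannot be estimated from the documents. The conclusion assumes that staff apply Section 7.7 as written and that no unpublished form instruction marks the date as administrative.

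**What to change.** 1. Add an AE outcome status for ongoing at Day 14 or at last contact, and leave the resolution date blank for these events.
2. State that anything reported about such an event at the Day 30 AE query already planned updates the existing record and does not open a new event. The one-event condition in Section 7.2 is then still met, and the duration is either closed at its true date or shown as censored at last contact.
3. Reconcile Sections 7.2 and 7.7, and state which rule governs unexpected events judged related and those on which PI and participant disagree.

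How long such events are actively followed is for the sponsor and investigators to decide; the change concerns only what is recorded. The cost is one form code and a wording amendment, with no added contacts.

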7.8 Safety Monitoring

7.8.1 Data Safety Monitoring Board

The Data Safety Monitoring Board (DSMB) will function as an independent oversight committee charged with overseeing participant safety and providing recommendations to the PIs and Co-investigators regarding the continuing conduct of the study. The DSMB will review periodic blinded Safety Reports. Unblinded but sealed Safety Reports will be available to each DSMB member, should the committee determine that review of unblinded safety data is warranted.

The DSMB will include independent individuals not involved in this research study and is comprised of members [name] (community representative), [name] (physician), [name] (probiotics and microbiome physician-scientist) and Chair, [name] (statistician). No member of the Committee has collaborated or co-published with the PIs within the past three years. They are qualified to review the patient safety data generated by this study because of their unique expertise. The clinical PI ([name]) and research team will provide the DSMB with an up-to-date data set to ensure safety, effective data collection and progress. During the course of the study, the DSMB will meet regularly to review adverse events data and approve continuation of the protocol.

7.8.2 Safety Reports

Study progress and safety will be reviewed 25%, 50% and 75% data completion (and more frequently if needed). Progress reports, including patient recruitment, retention/attrition, and AEs will be provided to the DSMB. A Safety Report will be compiled and will include a list and summary of AEs. In addition, the reports will address (1) whether AE rates are consistent with pre-study assumptions; (2) reason for dropouts from the study; (3) whether all participants met entry criteria; (4) whether continuation of the study is justified on the basis that additional data are needed to accomplish the stated aims of the study; and (5) conditions whereby the study might be terminated prematurely. The report will be sent to the DSMB and will be forwarded to the IRB and NCCIH. The IRB and other applicable recipients will review progress of this study on an annual basis.

The study team will generate Study Reports for the DSMB and will provide information on the following study parameters: the status of followups, adverse events and enrollment updates. Study Report tables will be generated only from aggregate (not by group assignment) baseline and aggregate safety data for the study population.

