6.6 Blinding

Each participant will be randomly allocated in a 2:1 ratio to either BB-12-supplemented yogurt or an identical yogurt without the added BB-12 probiotic. Both contain the starter culture YF-L702 (a mixed culture of *Streptococcus thermophilus* and *Lactobacillus delbrueckii* subsp. *bulgaricus*). The yogurts are similar in taste and will have identical nutritional value, such as the same amount of calcium, protein, calories, etc. The yogurts are packed in identical packaging with six different bin numbers. The participants, PIs, research staff are all blinded to the treatment allocation.

The study statistician, [name], will generate three group-labels (e.g. A, B, C) where two groups are the same, e.g. A=C: BB-12 group, B: control group. [name] will be blinded to which two are the two treatment groups and which one is the control group. These groups will be considered as three arms before unblinding.

PSU will send yogurt in six bins with distinct numbers, two of which will be control yogurt and four will be the BB-12 yogurt. Only the researchers at Maryland will know which bin numbers correspond to 'group 1' and which correspond to 'group 2', but will not know which is the active or control. PSU and Maryland have no contact with participants and will not release this information to the study team until the analyses are completed and databases are locked.

All study personnel at Georgetown and [name] will remain blinded throughout the study until the databases are locked. In the unfortunate event that a participant experiences a serious adverse event or emergency that requires unmasking the treatment groups, [name], a member of the Department of Family Medicine who is not affiliated with the study, will discuss the assignment and follow-up with the participant and their treating physician. [name] has done this for our previous clinical trials.

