7.4 Characteristics of an Adverse Event

7.4.1 Relationship to Study Intervention

To assess relationship of an event to study intervention, the following guidelines are used:

1. Related (Possibly Related, Probably Related, Definitely Related)
 - a. The event is known to occur with the study intervention.
 - b. There is a temporal relationship between the intervention and event onset.
 - c. The event abates when the intervention is discontinued.
 - d. The event reappears upon a rechallenge with the intervention.
2. Not Related (Unlikely Related, Not Related)
 - a. There is no temporal relationship between the intervention and event onset.
 - b. An alternate etiology has been established.

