8. INTERVENTION DISCONTINUATION

Study enrollment and/or interventions may be temporarily suspended or terminated if:

- Any study participant experiences death that the DSMB, PIs or IRB believes may be related to the study interventions.
- If a statistically or clinically significant number of SAEs or hospitalizations occur that the DSMB believes may be related to the treatment.
- New information from outside studies reveals that it would be unethical to continue enrolling participants in the study.
- The IRB decides that the study should be stopped.
- If statistical differences among the primary outcomes will be determined that require stopping. For example, if the differences among certain interventions make it unethical to continue or if the effect size is so small that it is implausible a positive outcome could occur.

A safety review by the DSMB, IRB, and/or NCCIH will be convened to determine if the study should continue per protocol, proceed with enhanced monitoring, be further investigated, be discontinued, or be modified and then proceed. The FDA and NCCIH retain the authority to suspend additional enrollment and study interventions and administration of study product for the entire study, as applicable.

This study will be stopped prior to its completion if:

- (1) the intervention is associated with adverse effects that call into question the safety of the intervention;
- (2) difficulty in study recruitment or retention will significantly impact the ability to evaluate the study endpoints;
- (3) any new information becomes available during the trial that necessitates stopping the trial; or
- (4) other situations occur that might warrant stopping the trial.

Individuals may be withdrawn from the study for any of the following:

- Adverse events; the clinical PI [name] will discuss AEs with the participant, and possibly with their personal physician, as needed, to determine whether the participant should be withdrawn from the study.
- If participant are deemed to be noncooperative (e.g. refuse to participate in follow-up calls or fail to complete diaries).
- If participants are lost to followup, i.e. more than 7 days without contact with study personnel during the follow-up period.
- Participant will not be withdrawn from the study solely for missed interventions or specimen collections, but may be withdrawn for non-cooperation or lost to follow-up.

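### Routine DSMB tables pool the arms and relatedness is graded once for yogurt plus antibiotic, so routine safety review cannot separate a BB-12 effect from the antibiotic

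*Combined protocol and SAP*

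**What the plan says.** Section 7.8.2 schedules safety reviews at 25%, 50% and 75% of data completion, with more if needed. On content it says "Study Report tables will be generated only from aggregate (not by group assignment) baseline and aggregate safety data for the study population". Section 7.8.1 gives the default: "The DSMB will review periodic blinded Safety Reports". Among the questions the reports must address is "whether AE rates are consistent with pre-study assumptions", with no rate attached.

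There is a route to the arms. Section 7.8.1 says "Unblinded but sealed Safety Reports will be available to each DSMB member, should the committee determine that review of unblinded safety data is warranted". Section 6.6 blinds the recruiting site's staff and splits the code between the product site and the Maryland group, who "will not release this information to the study team until the analyses are completed and databases are locked". It also says the statistician will work with three masked labels (A, B, C), two of them BB-12.

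Section 8 lists as a reason to stop that "the intervention is associated with adverse effects that call into question the safety of the intervention".

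On causality, the first guideline for a related event in section 7.4.1 is "The event is known to occur with the study intervention", with one intervention in view. The table in section 5.1 lists the study interventions as yogurt and amoxicillin-clavulanate together in each arm. Section 7.5 sets out expected risks by product, with diarrhea under both. The second section numbered 7.6.1 (Adverse Event Reporting) handles anticipated or unrelated SAEs less urgently, with annual reporting to NCCIH.

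**The concern.** The question specific to this trial is whether BB-12 adds harm on top of the antibiotic. Because both arms take amoxicillin-clavulanate and share an overlapping list of expected gastrointestinal events, only a comparison between arms can answer it. The routine tables remove that comparison. The stopping reason in section 8 depends on an association with the intervention that those tables cannot show for BB-12.

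The single relatedness grade has a similar effect at event level. A gastrointestinal event in days 1-7 can be called related through the antibiotic alone, so the record says nothing about the yogurt. Expectedness in section 7.4.2 is likewise judged for the intervention as a whole. An event listed in section 7.5 only for the antibiotic, such as nausea or *C. difficile* infection, could therefore count as anticipated whatever caused it, and that affects how fast an SAE is reported.

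The sealed report is the natural safeguard, but the information that would ordinarily prompt the board to open it is the pooled table.

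**Working it through.** **The plan's own figure.** The documents give no threshold, power or sample size for safety monitoring, so there is nothing to reproduce.

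**Inputs.** Allocation 2:1, 40 BB-12 and 20 control (section 6.5.3). Diarrhea rates: 15% anticipated in this trial (section 3.2), 20-35% with antibiotics (section 2.7), 5-35% (Appendix 4). Assumptions of this review: BB-12 doubles the control rate; the looks fall at 15, 30 and 45 of 60 participants; each look is split exactly 2:1.

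**Pooled rate.** With control rate p and BB-12 rate 2p, the pooled rate is (p + 2 × 2p)/3 = 5p/3.

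| Control | BB-12 | Pooled | Expected events in 60 | Inside 20-35%? |
|---|---|---|---|---|
| 10% | 20% | 16.7% | 10 | no, below |
| 15% | 30% | 25.0% | 15 | yes |
| 20% | 40% | 33.3% | 20 | yes |
| 25% | 50% | 41.7% | 25 | no, above |
| 35% | 70% | 58.3% | 35 | no, above |

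Solving 5p/3 = 0.20 and 5p/3 = 0.35 gives p = 12% and p = 21%. A doubling is hidden inside 20-35% only for control rates in that band. Against 5-35% the lower edge falls to 0.05 × 3/5 = 3%.

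**Chance that the observed pooled rate is at or below 35%** (exact convolution of two binomials):

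| Scenario | n=15 | n=30 | n=45 | n=60 |
|---|---|---|---|---|
| 15% vs 30% | 86% | 90% | 93% | 97% |
| 20% vs 40% | 62% | 59% | 57% | 67% |

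**Judged instead against the 15% planning rate.** A doubling from 15% gives 15 expected events where 60 × 0.15 = 9 were planned. An illustrative exact one-sided 5% flag on the pooled count (at least 6/15, 9/30, 12/45, 15/60), each look taken alone, fires with probability 14.5%, 32.5%, 45.4% and 55.1%.

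**What by-arm tables would show.** For 15% vs 30%, the final expected counts are 3/20 on control and 12/40 on BB-12. If the two BB-12 labels are of equal size, the masked table shows 3, 6 and 6 of 20. The pooled table shows 15/60. Power of the two-sided 5% Fisher test, counting results in the direction of harm:

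| Scenario | 5 v 10 | 10 v 20 | 15 v 30 | 20 v 40 |
|---|---|---|---|---|
| 15% vs 30% | 2% | 6% | 14% | 19% |
| 20% vs 40% | 6% | 13% | 21% | 29% |

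For 80% power (normal approximation, 2:1) the trial would need 93 + 186 or 63 + 126 participants.

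**The sealed report.** Section 7.8.1 promises it to each DSMB member. Section 7.8.2 gives Study Reports to the study team, and section 6.6 bars release of the code to that team before lock. No section assigns an unblinded report to anyone else or says when the board should open it.

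**Illustration from the sponsor's own studies (section 2.10).** Pediatric study, days 0-10: 61 events in 29 children on BB-12 and 35 in 31 on control, pooled 96. Adult study: 67 events in 19 on BB-12 and 98 in 21 on control, pooled 165. The directions are opposite, and neither can be read from the pooled totals. These are event counts, not participants.

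**The case against.** A reader might infer that the DSMB cannot see a BB-12 signal at all. The documents do not support that: section 7.8.1 attaches no precondition to opening the sealed reports beyond the board's own judgment, so it could open them at its first review.

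A reader might also infer that section 6.6 makes the sealed report impossible to prepare. It does not. The bar is on release to the study team; the DSMB is independent of that team, and section 6.6 itself provides for emergency unmasking through someone unaffiliated with the study. What remains is that nobody is assigned to prepare the report.

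A third tempting reading is that pooled counts carry no information. Section 3.2's 15% is the only rate projected for these participants, and against it a pooled 25% is a visible excess. The earlier adult study had diarrhea in 4/40 (10%), which would make 25-33% stand out further. This stands, but section 7.8.2 does not say which rate applies, and even the 15% benchmark misses a doubling from 15% more often than not at each scheduled look (85.5%, 67.5%, 54.6%).

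It is also fair to say that the aggregate-only sentence governs Study Report tables, while Safety Reports are described only as blinded, which need not exclude masked-arm tables. But no section provides such tables, and the Safety Report also goes to the IRB and NCCIH.

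On causality, section 7.5 already separates risks by product, days 8-14 are yogurt without antibiotic, and grading an early event as related errs toward reporting. The AE form is not reproduced and may already have per-product fields; the protocol does not require them. For diarrhea itself, per-product expectedness would read the same for both products. The gain there is in relationship, and in events listed for one product only.

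Finally, SAEs reach the principal investigators and IRB case by case without any pooled table, and the study claims no power for diarrhea. Both are correct and limit the weight of the point.

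**Conclusion.** The point holds in limited form. On the tables the plan describes, routine DSMB review cannot separate a BB-12 effect from the antibiotic, and the protocol does not require relatedness to be recorded separately for each. A doubling pools to 25% (from 15%) or 33% (from 20%), inside section 2.7's range. That masking depends on the assumed doubling, on 2:1 allocation, on control rates of about 12-21%, and on 20-35% being the benchmark. It should not be read as general, nor as meaning that the board is shut out of by-arm data. The sealed report is permitted but lacks a trigger and a named preparer. The change is worth making because it is cheap; it would make an imbalance visible, not statistically detectable.

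**What to change.** 1. In section 7.8.2, add a closed-session DSMB table of AEs and SAEs by the masked A/B/C labels of section 6.6. Keep pooled tables for the open report to the IRB and NCCIH. The board then has by-label information on which to decide whether to open the key.
2. Reconcile sections 6.6 and 7.8.1 by naming a party outside the study team, such as the code holder at the product site, to prepare the sealed key or report for the DSMB.
3. On the AE form, and in sections 7.4.1 and 7.4.2, record relationship and expectedness separately for yogurt and for amoxicillin-clavulanate.
4. State which diarrhea rate (15%, 20-35% or 5-35%) is the pre-study assumption that section 7.8.2 uses.

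Describe the by-label tables as descriptive, with no formal test. The cost is one extra table per review, an extra field or two on the form, and a small risk that whoever prepares the table guesses a label from a large imbalance.
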